6.2 Radiology

1. MRI magnet strength	1.5 T only
RF field	Approximately 64 MHz
Maximum spatial gradient	20T/m (2,000 G/cm)
MRI equipment specification	Horizontal, 1H proton, closed bore scanners only
2. Specific Absorption Rate (SAR) limits for the entire active scan	Normal Operating Mode ^a : 
 • Whole body averaged, ≤ 2.0 watts/kilogram (W/Kg) • Head, ≤ 3.2 W/Kg
3. Maximum specified gradient slew rate	≤ 200 T/m/s per axis
4. The use of receive-only coils is not restricted. Local transmit-only coils or local transmit/receive coils may be used, but should not be placed directly over the defibrillation system. 5. Patient in supine or prone position only 6. Patient must be continuously monitored by pulse oximetry and electrocardiography (ECG) for the entire duration in which the pulse generator is in MRI Protection Mode. Ensure backup therapy is available (external rescue).	
^a. As defined in IEC 60601-2-33, 201.3.224, 3rd Edition.	

7. Objectives

The objective of the study is to collect data to confirm the safety and effectiveness of the ImageReady MR Conditional Defibrillation System when used in the 1.5T MRI environment under the labeled Conditions of Use.

Additionally, the study will assess medically necessary MR scans according to the labeled Conditions of Use to provide real-world scanning data.

The study also aims to demonstrate the continued ability of the ImageReady MR Conditional Defibrillation System to sense and detect VF post MRI scan by collecting and analyzing data from spontaneous VF episodes, “for-cause” VF inductions, and from an optional VF induction Sub-study.

8. Endpoints (Phase I only)

For details around Phase I endpoints, see Section 13.1.

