9.2 Justification for the Study Design

The ENABLE MRI Study is being conducted to collect data to support pre-market regulatory agency submissions for approval of the ImageReady System for use in the 1.5T MRI environment (Phase I), in geographies where prospective clinical data is required. The study data will also be used to support worldwide post-market requirements in certain geographies.

The study is designed with one interim analysis to support regulatory submissions.

The study also aims to demonstrate the continued ability of the ImageReady™ MR Conditional Defibrillation System to sense and detect VF post MRI scan by collecting and analyzing data from spontaneous VF episodes, “for-cause” VF inductions, and from the VF induction Sub-study.

Phase I and Phase II data will be used to evaluate VT/VF sensing after an MR scan, potential influence of multiple MR scans on the ImageReady System, Beeper functionality after MR scans, and programming of the MRI Protection Mode (see Section 13.2 on ancillary analysis).

Data from the FINELINE II leads will be used to support regulatory approval in geographies that do not already have market approval of FINELINE II as an MR Conditional lead.

10. Subject Selection

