12.1 Data Collection

A detailed list of procedures, testing and data collected required at the study visits are presented in Table 12-1. The table also has the study visits that are needed per study phase and per implanted device status.

- For Phase I subjects there will be a non-diagnostic study required MR scan (during the MRI visit)
- For Phase I subjects, the MRI and the MRI + 1 Month visits are required.
- For VF Induction Sub-Study subjects, VF Induction testing will be performed at the MRI + 1 Month Visit
- For "for cause" VF induction subjects, VF Induction testing will be performed ideally at the MRI + 1 Month Visit or up to 14 calendar days later
- For de novo implants (phase I), the Implant and Pre-discharge visits are required.

Table 12-1: Data Collection Schedule

Procedure / Assessment	Screening and Enrollment	Phase I: De novo implants only		Phase I only		Every Three-Month Visits***	Every Annual Visits*	Additional Visits	Medically necessary MRI
		Implant	Pre-Discharge	MRI Visit	MRI + 1 Month Visit				
Timeframe	De novo: ≤ 30 days prior to Implant Existing implant	Implant	3-72 hours from Implant	De novo: 6-9 weeks from Implant ^Δ Existing implant: within 6 weeks from Enrollment ^Δ	30 ± 7 days from MRI Visit	90 ± 30 days from MRI Visit	De novo: 365±90 days* from implant Existing implant: 365±90 days* from Enrollment	--	--
Informed consent form and process, including informed consent signature and date	X**	--	--	--	--	--	--	--	--
12 lead ECG & 10s rhythm strip	X (document exclusion #5)	--	--	X Pre MRI (HR monitoring)	--	--	--	--	X Pre MRI (HR monitoring)
Demographics	X	--	--	--	--	--	--	--	--
Physical assessment	X	--	--	--	--	--	--	--	--
Medical History, Comorbidities, Cardiac Disease History, Medications	X	--	--	--	--	--	--	--	--
ICD/CRT-D system implant	--	X	--	--	--	--	--	--	--
Device Evaluation (includes pace thresholds, intrinsic amplitudes, impedances, RV shock impedance)	--	X	X	X Pre & Post	X	X	X	O	O

Procedure / Assessment	Screening and Enrollment	Phase I: De novo implants only		Phase I only		Every Three-Month Visits***	Every Annual Visits*	Additional Visits	Medically necessary MRI
		Implant	Pre-Discharge	MRI Visit	MRI + 1 Month Visit				

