12.7.4 Device Evaluation after the MR Scan

1. All implanted leads will be evaluated within two hours upon exit from the MRI Protection Mode through the implanted PG **for THREE separate consecutive sets of measurements** using the test parameters listed in Table 12-3:
 - Manual pacing threshold tests, as defined in sections 12.5.1.1, 12.5.1.2 and 12.5.1.3. Sensing amplitude
 - Impedance
 - Shock impedance (RV lead only)
2. Test for phrenic nerve stimulation (PNS) and measure the PNS threshold if detected in the programmed LV lead configuration
3. Perform an assessment of Beeper function as defined in section 12.7.1.1. After performing the assessment of the Beeper, if the Beeper is audible, the user may choose to manually re-enable the Beeper.

Record the measurements in the EDC system.

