12.12 Medically Necessary MRI Visits

During the study, if a subject needs a medically necessary MR scan, BSC recommends the subject be directed to have the scan at the Study site.

Note: In case the medically necessary MR scan is performed at a non-investigational site, all efforts must be made to collect the data and adhere to the MRI Conditions of Use.

Study flow is identical to the MRI visit as described in section 12.7. Some data collection is optional for Medically Necessary MRI visit as shown in italic in Table 12-11.

For medically necessary MRI scans, all activities performed by the site Principal Investigator or a sub-investigator at the MRI visit (i.e. heart rhythm monitoring, hemodynamic monitoring) can be performed by a trained and qualified Health Care Professional (HCP).

As for the MRI visit, it is recommended to have a programmer powered ON in Zone II near the MRI room in case the patient develops the urgent need for pacing.

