Save All	Retain the original at the center and submit a copy to Boston Scientific

Text in table that is italicized is recommended

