13.2.5 Assessment of Effect of Medically Necessary MR Scans

Boston Scientific proposes to collect available data on medically necessary MR scans (MNS) from Phase I and II subjects over a 3-year follow-up period. A summary of changes in lead measurements pre- to post- MNS and any MNS related complications will be presented.

To assess the additive effect of multiple MR scans, the same summaries will be done for subjects with multiple MR scans.

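### Section 13.2.5 sets out to assess the additive effect of multiple MR scans but specifies only the change across each single scan, leaving out change between scans and from first to last

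*Combined protocol and SAP*

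**What the plan says.** Section 9.2 lists, among the uses of the Phase I and Phase II data, the "potential influence of multiple MR scans on the ImageReady System". Section 7 gives the wider aim: "the study will assess medically necessary MR scans according to the labeled Conditions of Use to provide real-world scanning data".

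Section 13.2.5 covers medically necessary scans (MNS) with whatever data are available over three years. Its summary is defined in one sentence: "A summary of changes in lead measurements pre- to post- MNS and any MNS related complications will be presented". The next sentence extends it: "To assess the additive effect of multiple MR scans, the same summaries will be done for subjects with multiple MR scans". No other lead analysis of repeated scanning is described in the readable text.

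On data collection:

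- In Table 12-1 the row beginning "Device Evaluation (includes pace thresholds, intrinsic amplitudes, impedances, RV shock impedance" is marked optional in the medically necessary MRI column.
- Section 12.12 gives an MNS the same flow as the Phase I MRI Visit, but adds: "Some data collection is optional for Medically Necessary MRI visit as shown in italic in Table 12-11". The lead tests before and after the scan are both in italics, and the note under the table reads: "Text in table that is italicized is recommended".
- If the MNS lead tests are done, the flow of 12.7 applies. Section 12.7.4 sets the timing of the post-scan test: "All implanted leads will be evaluated within two hours upon exit from the MRI Protection Mode".

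**The concern.** An assessment of additive effect should show where a lead stands after several scans compared with where it stood before any of them. Repeating a one-scan summary in subjects who had several scans answers a narrower question: whether each scan was followed, within about two hours, by a change.

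Two things are left unsummarised: change that appears after the post-scan test and before the next scan, and the total from first to last. Because MNS lead tests are optional, the measured scans may also be a selected group, and 13.2.5 does not ask how many scans lack paired values. A report that followed the text exactly could state that no additive effect was seen without having tabulated the quantity that would show one.

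**Working it through.** There is no planned figure to reproduce. The readable text gives no sample size or expected number of multi-scan subjects for this assessment. The check sets the stated aim beside the specified summary and then beside the data.

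**Step 1: the quantity.** For two scans, write d1 and d2 for the change across each scan and b for the change from the test after scan 1 to the test before scan 2. Then

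cumulative change = d1 + b + d2.

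For k scans there are k terms d and k − 1 terms b. Section 13.2.5 specifies the d terms for MNS. It specifies neither the b terms nor the sum.

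**Step 2: what is and is not visible.** These values are assumptions for illustration, not predictions.

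- Rise of 0.3 V at each of two scans, b = 0: the table shows 0.3 V and 0.3 V. The rise is visible; the total of 0.6 V is not tabulated.
- No rise within two hours of either scan, b = 0.4 V: the table shows 0 and 0, while the cumulative change is 0 + 0.4 + 0 = 0.4 V.

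The real loss is therefore in the second case.

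**Step 3: which lead tests exist around a later scan.**

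- *Phase I, study scan.* Three sets before the scan (12.7.1), three after it (12.7.4) and three at 30 ± 7 days (12.8.1) are required, with thresholds at 0.5 ms and the same LV configuration at the MRI and MRI + 1 Month visits (Table 12-3). An expected need for an earlier MNS is an exclusion (criterion 4), so an MNS normally comes after all of these. The first-scan baseline is secured, but 13.2.5 does not say that it serves as the baseline for later scans, or that the study scan counts as one of the multiple scans.
- *Phase II, existing implants.* In the readable text no device evaluation is required at enrollment (Table 12-1). Section 10.2 asks only that impedances be in range and that there be no evidence of lead or generator failure.
- *After an MNS.* No one-month visit is tied to it. Three-monthly follow-up is strongly recommended (12.9); Table 12-1 requires the data if the visit takes place. Annual visits are required, with threshold test parameters left to the physician (12.10.1).

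**Step 4: spacing of the required annual tests.** The windows are 365 ± 90, 730 ± 90 and 1095 ± 90 days, that is 275–455, 640–820 and 1005–1185. Successive visits are nominally 365 days apart. The longest permitted interval is 820 − 275 = 545 days, and likewise 1185 − 640 = 545. That needs one visit at its earliest limit and the next at its latest, and it ignores the recommended three-monthly checks.

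**Step 5: why settings matter if annual thresholds are used.** Assume a threshold follows V = Vr(1 + c/PW), where Vr is a constant, PW is the pulse width and c is 0.2–0.6 ms (an assumed range). A lead at 1.0 V with 0.5 ms then reads 0.07 to 0.14 V higher at 0.4 ms and 0.14 to 0.27 V lower at 1.0 ms, with no true change. Thresholds at other pulse widths should not enter a cumulative change.

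**The case against.** The strongest case on the other side has four parts.

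*The text applies no cut-off.* A reader might infer that small stepwise rises at each scan would be hidden. The documents do not support this. The 0.5 V, 1.0 V and 50% limits belong to the primary effectiveness endpoints (13.1.2 to 13.1.5); 13.2.5 reports changes, so per-scan rises would be seen. This part stands in full, and the point here is confined to between-scan change and the total.

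*The data are better than they look.* A reader might also infer that nothing usable is collected. That is not so. Phase I has a required fixed-setting baseline and one-month test, three-monthly data are required if the visit occurs, and annual Save All files go to the sponsor. Section 5.1.1 also lists daily lead diagnostics that are suspended only in MRI Protection Mode. This stands as well, but it strengthens the case for linking these values, which 13.2.5 does not do.

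*Optional testing is deliberate.* MNS are clinical scans, sometimes at non-study sites, and the aim is real-world data. This stands: the documents give no ground for making the tests mandatory. It makes reporting the number of unmeasured scans more important.

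*A paired test around the scan isolates the scan effect better.* Change over up to three years also reflects lead ageing and disease, and there is no unscanned control. This is true, and it is why the per-scan change should be kept and no causal claim made. The text does not forbid a cumulative summary, and comparing per-scan changes in multi-scan subjects with those in all scanned subjects would be informative. Neither supplies the missing quantities.

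**Conclusion.** The point holds as a mismatch between a stated aim and the summary specified for it. Following 13.2.5 as written gives the per-scan changes where measured. It gives neither the k − 1 between-scan changes nor the total, and no denominator of scans without paired values. The remedy is a concrete addition and costs almost nothing.

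It is minor. Section 13.2 describes the ancillary assessments as informal and unpowered, no primary endpoint changes, and MNS-related complications are summarised in any case. A reader might want to state what share of Phase II scans would lack a baseline. The readable text gives neither the number nor the timing of such scans, so no such share can be derived.

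The conclusion rests on reading the same summaries as the one just defined in 13.2.5, and on the readable text only. Section 11.1.2 and much of 9.1 and 11.4 are redacted, which matters most for what is said about Phase II.

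**What to change.** Amend the SAP under 13.5.5, with no protocol amendment. In 13.2.5, for subjects with two or more scans and counting the Phase I study scan, add descriptive summaries of:

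- (a) cumulative change, from the value before the first scan to the first lead test after the last scan. Use the post-scan set if taken, otherwise the next three-monthly or annual value. Include thresholds only if recorded at 0.5 ms and, for LV, in the same configuration.
- (b) change across each scan.
- (c) change between one scan's post-scan test and the next scan's pre-scan test.

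For each measure, report the number of scans, the number with paired values, the source of each value and the days since the last scan. State that no causal conclusion is drawn, because there is no unscanned control and cumulative change also reflects lead ageing and disease.

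The cost is a paragraph of SAP text and one table, with no added visit, test or burden on subjects or sites. The limits are that few subjects may have several scans, values not collected cannot be recovered, and the result stays descriptive.

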13.2.6 Assessment of Beeper Function

As the beeper function may be affected by the MR Scanner static magnet field, beeper functionality will be summarized using descriptive statistics, for pre- and post-scan, for both the study required MR scans and MNS scans.

13.2.7 Assessment of Programming the MRI Protection Mode

In order to understand the use of the MRI Protection Mode, the following time durations will be summarized using descriptive statistics for both study-related MR scans and medically necessary MR scans:

- Duration of the PG in the MRI Protection Mode
- Time from the start of the MRI Protection Mode to the start of the MR scan
- Time from the end of the MR scan to exiting the MRI Protection Mode

13.2.8 Assessment of Image Artifacts for non-medically necessary MR scans

The image artifact core laboratory will evaluate the MR scan image artifacts in a subset of the non-medically necessary MR scan images from Phase I of the study. The results from the core lab analysis will be summarized in the study report.

13.3 Sample Size Summary

The study will enroll a total of 500 subjects.

The estimated sample size for Phase I is based on the following assumptions:

The sample size for the whole study was chosen at up to 500 subjects in order to observe 30 spontaneous VT/VF episodes post MRI scan.

13.4 General Statistical Methods

13.4.1 Control of Systematic Error/Bias

Selection of patients will be made from the Investigator's usual patient load. All patients meeting the eligibility criteria and having signed the ICF will be eligible for enrollment in the study. To control for inter-observer variability among sites, an independent Clinical Events Committee (CEC) will determine the MR Scan-related ImageReady System complications to be used in the analysis of the Primary Safety Endpoint.

13.4.2 Control of Type I Error

Each primary effectiveness endpoints can be tested at the significance level of 5% and the primary safety endpoint can be tested at the significance level of 2.5% while still maintaining the overall type I error level at no greater than 5%. This follows the methodology of the Intersection-Union Test (IUT).

13.4.3 Number of Subjects per Investigative Site

To avoid any center effect and bias, one center will not be authorized to implant or attempt more than 100 subjects (20% of the maximum number of subjects).

13.5 Data Analyses

The following data analyses are planned for the ENABLE MRI Clinical Study:

13.5.1 Interim Analyses

No formal interim analyses are planned for the purpose of stopping the study early for declaring effectiveness or for futility. The interim analysis being conducted on 20 subjects is to support regulatory requirements and submissions. Analysis of each endpoint will be performed when all applicable data for that endpoint has been collected.

13.5.2 Pooling Analyses

13.5.2.1 Assessment of Pooling Across Device Type

The single chamber ICDs and the CRT-Ds are expected to perform similarly regarding any effect of MRI on RV pacing threshold or RV sensed amplitude as well MR Scan-related complications. Any effects of MRI on tissue surrounding each respective electrode design are expected to be proportionally similar. Therefore, device (PG and lead) type will be pooled for the analyses of all endpoints. Additionally, analysis will be performed for each of the primary safety and effectiveness endpoints 1 and 2 to verify poolability. To assess the impact of device type on each endpoint, a likelihood ratio test from a regression model will be conducted. The regression model may include additional baseline covariates to attempt to adjust for any imbalances between the device type groups, and will examine the effect of device type. The following baseline covariates may be considered for inclusion: age, gender, height, weight and geography. The likelihood ratio test will compare the log likelihoods between a model containing device type as a covariate and a model not containing device type as a covariate. The test will be performed at an α equal to 15%. Endpoint results will be presented for each device type regardless of the poolability analysis results.

13.5.2.2 Assessment of Pooling Across Geographies and Investigational Centers

In addition to testing the poolability of data by device type, the poolability of data by geography and investigational center will be tested. These analyses will be performed to determine whether there are differences between the US and international geographies, and from center-to-center.

A minimum of 50% of Phase I patients will be from the US. Center-to-center heterogeneity will be assessed for each endpoint by performing random effects logistic regression analyses. Centers enrolling 5 subjects or fewer will be combined within region (US versus OUS) into pooled sites of 6 or more subjects for the purpose of this pooling analysis.

Investigational center will be added into the model as a random effect. Centers will be deemed to be heterogeneous if the variance of the random center effect is found to significantly differ from zero. A significance level of 15% will be used for each test.

13.5.2.3 Assessment of Pooling Across protocol versions

The inclusion/exclusion criteria have been updated with version AE. The poolability of data of subjects enrolled under version AE or later will be compared to subjects enrolled under all prior versions of the protocol.

To assess the impact of the protocol version on each endpoint, a likelihood ratio test from a regression model will be conducted. The regression model may include additional baseline covariates to attempt to adjust for any imbalances between the device type groups, and will examine the effect of protocol version. The following baseline covariates may be considered for inclusion: age, gender, height, weight and geography. The likelihood ratio test will compare the log likelihoods between a model containing protocol version as a covariate and a model not containing protocol version as a covariate. The test will be performed at an α equal to 15%. Endpoint results will be presented for each protocol version regardless of the poolability analysis results.

13.5.3 Subgroup Analyses

Analyses will be performed for each primary endpoint to determine whether significant differences exist in endpoint results between subgroups. The list of subgroups (with applicable definitions in parentheses) includes, but is not necessarily limited to:

- Device Type (Single Chamber ICD vs. CRT-D) – note that this analysis will not be done for Primary Effectiveness Endpoint 3 or 4,
- Sex (Female vs. Male),
- Geography (International vs. United States),
- Age (< 65 years vs. \geq 65 years).

The subgroup variable will be added to a logistic regression model. For effectiveness endpoints, treatment and an interaction term of subgroup and treatment will be added as well. A test for significance at the 15% level will be performed. For each subgroup variable in which a significant difference exists, the results for each subgroup will be presented separately. BSC does not plan to seek labeling for these subgroups based on these analyses.

